8.4.3 Safety Analyses

All recorded adverse events will be listed and tabulated by system organ class, preferred term and treatment. Vital signs and clinical laboratory test results will be listed and summarized by treatment. Any significant physical examination findings, and clinical laboratory results will be listed. ECG readings will be evaluated by the investigator and abnormalities, if present, will be listed.

8.4.4 Pharmacokinetic Analyses

Ctrough will be summarized by time for BMS-986165 in subjects with moderate to severe psoriasis. Additional details will be provided in the statistical analysis plan (SAP) as necessary.

[REDACTED]

[REDACTED]

8.4.7 Outcomes Research Analyses

Not applicable.

8.4.8 Other Analyses

8.4.8.1 Population PK and Exposure Response Analysis

Analysis of PK and exposure-response relationships of BMS-986165 will be conducted using a population approach as appropriate and reported separately from the clinical study report.

8.5 Interim Analyses

There are no planned interim analyses for the current study.

9 STUDY MANAGEMENT

9.1 Compliance

9.1.1 Compliance with the Protocol and Protocol Revisions

The investigator should not implement any deviation or change to the protocol without prior review and documented approval/favorable opinion of an amendment from the IRB/IEC (and if applicable, also by local health authority) except where necessary to eliminate an immediate hazard(s) to study subjects.

If a deviation or change to a protocol is implemented to eliminate an immediate hazard(s) prior to obtaining relevant approval/favorable opinion(s) the deviation or change will be submitted as soon as possible to:

- IRB/IEC

- Regulatory Authority(ies), if applicable by local regulations per national requirements

Documentation of approval/favorable opinion signed by the chairperson or designate of the IRB(s)/IEC(s) and if applicable, also by local health authority, must be sent to BMS.

If an amendment substantially alters the study design or increases the potential risk to the subject: (1) the consent form must be revised and submitted to the IRB(s)/IEC(s) for review and approval/favorable opinion; (2) the revised form must be used to obtain consent from subjects currently enrolled in the study if they are affected by the amendment; and (3) the new form must be used to obtain consent from new subjects prior to enrollment.

If the revision is done via an administrative letter, investigators must inform their IRB(s)/IEC(s).

9.1.2 Monitoring

BMS or designate representatives will review data centrally to identify potential issues to determine a schedule of on-site visits for targeted review of study records.

Representatives of BMS must be allowed to visit all study site locations periodically to assess the data quality and study integrity. On site they will review study records and directly compare them with source documents, discuss the conduct of the study with the investigator, and verify that the facilities remain acceptable. Certain CRF pages and/or electronic files may serve as the source documents: .

In addition, the study may be evaluated by BMS or designate internal auditors and government inspectors who must be allowed access to CRFs, source documents, other study files, and study facilities. BMS audit reports will be kept confidential.

The investigator must notify BMS promptly of any inspections scheduled by regulatory authorities and promptly forward copies of inspection reports to BMS or designate.

9.1.2.1 Source Documentation

The Investigator is responsible for ensuring that the source data are accurate, legible, contemporaneous, original and attributable, whether the data are hand-written on paper or entered electronically. If source data are created (first entered), modified, maintained, archived, retrieved, or transmitted electronically via computerized systems (and/or any other kind of electronic devices) as part of regulated clinical trial activities, such systems must be compliant with all applicable laws and regulations governing use of electronic records and/or electronic signatures. Such systems may include, but are not limited to, electronic medical/health records (EMRs/EHRs), adverse event tracking/reporting, protocol required assessments, and/or drug accountability records).

When paper records from such systems are used in place of electronic format to perform regulated activities, such paper records should be certified copies. A certified copy consists of a copy of original information that has been verified, as indicated by a dated signature, as an exact copy having all of the same attributes and information as the original.

9.2 Records

9.2.1 *Records Retention*

The investigator (or head of the study site in Japan) must retain all study records and source documents for the maximum period required by applicable regulations and guidelines, or institution procedures, or for the period specified by BMS or designate, whichever is longer. The investigator (or head of the study site in Japan) must contact BMS or designate prior to destroying any records associated with the study and BMS or designate will notify the investigator when the study records are no longer needed.

If the investigator withdraws from the study (e.g., relocation, retirement), the records shall be transferred to a mutually agreed upon designate (e.g., another investigator, study site, IRB). Notice of such transfer will be given in writing to BMS or designate.

9.2.2 *Study Drug Records*

Records for IP (whether supplied by BMS, its vendors, or the site) must substantiate IP integrity and traceability from receipt, preparation, administration, and through destruction or return. Records must be made available for review at the request of BMS/designate or a Health Authority.

If...	Then...
Supplied by BMS (or its vendors):•	
Records or logs must comply with applicable regulations and guidelines and should include:
 
 • amount received and placed in storage area • amount currently in storage area • label identification number or batch number • amount dispensed to and returned by each subject, including unique subject identifiers • amount transferred to another area/site for dispensing or storage • nonstudy disposition (e.g., lost, wasted) • amount destroyed at study site, if applicable • amount returned to BMS • retain samples for bioavailability/bioequivalence, if applicable • dates and initials of person responsible for Investigational Product dispensing/accountability, as per the Delegation of Authority Form.
Sourced by site, and not supplied by BMS or its vendors (examples include IP sourced from the sites stock or commercial supply, or a specialty pharmacy)	
The investigator or designate accepts responsibility for documenting traceability and study drug integrity in accordance with requirements applicable under law and the SOPs/standards of the sourcing pharmacy.
 
These records should include:
 
 • label identification number or batch number • amount dispensed to and returned by each subject, including unique subject identifiers • dates and initials of person responsible for Investigational Product dispensing/accountability, as per the Delegation of Authority Form.

BMS or designate will provide forms to facilitate inventory control if the investigational site does not have an established system that meets these requirements.

9.2.3 Case Report Forms

An investigator is required to prepare and maintain adequate and accurate case histories designed to record all observations and other data pertinent to the investigation on each individual treated or entered as a control in the investigation. Data that are derived from source documents and reported on the CRF must be consistent with the source documents or the discrepancies must be explained. Additional clinical information may be collected and analyzed in an effort to enhance understanding of product safety. CRFs may be requested for AEs and/or laboratory abnormalities that are reported or identified during the course of the study.

For sites using the Sponsor or designate electronic data capture tool, electronic CRFs will be prepared for all data collection fields except for fields specific to SAEs and pregnancy, which will be reported on the or electronic SAE form and Pregnancy Surveillance form, respectively. If electronic SAE form is not available, a paper SAE form can be used. Spaces may be left blank only in those circumstances permitted by study-specific CRF completion guidelines provided by BMS.

The confidentiality of records that could identify subjects must be protected, respecting the privacy and confidentiality rules in accordance with the applicable regulatory requirement(s).

The investigator will maintain a signature sheet to document signatures and initials of all persons authorized to make entries and/or corrections on CRFs.

The completed CRF, SAE/pregnancy CRFs, must be promptly reviewed, signed, and dated by the investigator or qualified physician who is a subinvestigator and who is delegated this task on the Delegation of Authority Form Subinvestigators in Japan may not be delegated the CRF approval task. For electronic CRFs, review and approval/signature is completed electronically through the BMS electronic data capture tool. The investigator must retain a copy of the CRFs including records of the changes and corrections.

Each individual electronically signing electronic CRFs must meet Sponsor or designate training requirements and must only access the BMS electronic data capture tool using the unique user account provided by Sponsor or designate. User accounts are not to be shared or reassigned to other individuals.

9.3 Clinical Study Report and Publications

A Signatory Investigator must be selected to sign the clinical study report.

For this protocol, the signatory investigator will be selected as appropriate based on the following criteria:

External principal investigator designated at protocol development

National coordinating investigator

Study steering committee chair or their designate

Subject recruitment (e.g., among the top quartile of enrollers)

Involvement in trial design

Regional representation (e.g., among top quartile of enrollers from a specified region or country)
Other criteria (as determined by the study team)

The data collected during this study are confidential and proprietary to BMS or designee. Any publications or abstracts arising from this study must adhere to the publication requirements set forth in the clinical trial agreement (CTA) governing [Study site or Investigator] participation in the study. These requirements include, but are not limited to, submitting proposed publications to BMS or designate at the earliest practicable time prior to submission or presentation and otherwise within the time period set forth in the CTA.

10 GLOSSARY OF TERMS

Term	Definition
Complete Abstinence	Complete Abstinence is defined as complete avoidance of heterosexual intercourse and is an acceptable form of contraception for all study drugs. This also means that abstinence is the preferred and usual lifestyle of the patient. This does not mean periodic abstinence (e.g., calendar, ovulation, symptothermal, profession of abstinence for entry into a clinical trial, post-ovulation methods) and withdrawal, which are not acceptable methods of contraception. Women must continue to have pregnancy tests. Acceptable alternate methods of highly or less effective contraception's must be discussed in the event that the subject chooses to forego complete abstinence.
Additional Research	Those scientific activities which cannot be reasonably anticipated at the time of trial design, for which we would like to collect and/or retain samples from study participants. Examples of additional research include, but are not limited to, new assay development and validation, companion diagnostic development, new hypotheses in the interaction of drug and the human body, and exploration of emerging science in the understanding of disease.

11 LIST OF ABBREVIATIONS

Term	Definition
AE	adverse event
ACLS	advanced cardiac life support
AI	accumulation index
AI_AUC	AUC Accumulation Index; ratio of AUC(TAU) at steady state to AUC(TAU) after the first dose
AI_Cmax	Cmax Accumulation Index; ratio of Cmax at steady state to Cmax after the first dose
AI_Ctau	Ctau Accumulation Index; ratio of Ctau at steady state to Ctau after the first dose
ALT	alanine aminotransferase
ANC	absolute neutrophil count
ANOVA	analysis of variance
aPTT	activated partial thromboplastin time
AR	Additional research
AST	aspartate aminotransferase
AT	aminotransaminases
AUC	area under the concentration-time curve
AUC(INF)	area under the concentration-time curve from time zero extrapolated to infinite time
AUC(0-T)	area under the concentration-time curve from time zero to the time of the last quantifiable concentration
AUC(TAU)	area under the concentration-time curve in one dosing interval
A-V	atrioventricular
BA/BE	bioavailability/bioequivalence
BID, bid	bis in die, twice daily
BLQ	below limit of quantification
BMI	body mass index
BMS	Bristol-Myers Squibb
BP	blood pressure
BSA	Body Surface Area

Term	Definition
BUN	blood urea nitrogen
C	Celsius
C12	concentration at 12 hours
C24	concentration at 24 hours
Ca ⁺⁺	calcium
Cavg	average concentration
CBC	complete blood count
Cexpected-tau	expected concentration in a dosing interval
CFR	Code of Federal Regulations
CI	confidence interval
Cl ⁻	chloride
CLcr	creatinine clearance
cm	centimeter
Cmax, CMAX	maximum observed concentration
Cmin, CMIN	trough observed concentration
CNS	Central nervous system
CRC	Clinical Research Center
CRF	Case Report Form, paper or electronic
Ct	Expected concentration at a certain time, usually at the end of an expected future dosing interval (e.g., concentration at 24 hours, concentration at 12 hours, etc.)
Ctau	Concentration in a dosing interval (e.g., concentration at 24 hours, concentration at 12 hours, etc.)
Ctrough	Trough observed plasma concentration
CV	coefficient of variation
CYP	cytochrome p-450
D/C	discontinue
dL	deciliter
DMC	Data monitoring committee
DLQI	Dermatology Quality Life Index
DSM IV	Diagnostic and Statistical Manual of Mental Disorders (4 th Edition)

Term	Definition
EA	extent of absorption
ECG	electrocardiogram
eCRF	Electronic Case Report Form
EDC	Electronic Data Capture
EEG	electroencephalogram
e.g.	exempli gratia (for example)
ESR	Expedited Safety Report
F	bioavailability
FDA	Food and Drug Administration
FSH	follicle stimulating hormone
g	gram
GC	gas chromatography
GCP	Good Clinical Practice
GGT	gamma-glutamyl transferase
GFR	glomerular filtration rate
h	hour
HBsAg	hepatitis B surface antigen
HBV	hepatitis B virus
HCV	hepatitis C virus
HCO ₃ ⁻	bicarbonate
HIV	Human Immunodeficiency Virus
HR	heart rate
HRT	hormone replacement therapy
ICD	International Classification of Diseases
ICH	International Council on Harmonisation
i.e.	id est (that is)
IEC	Independent Ethics Committee
IMP	investigational medicinal products
IND	Investigational New Drug Exemption
IRB	Institutional Review Board

Term	Definition
IU	International Unit
IV	intravenous
K	slope of the terminal phase of the log concentration-time curve
K ₃ EDTA	potassium ethylenediaminetetraacetic acid
K ⁺	potassium
kg	kilogram
L	liter
LAM	Lactation amenorrhea method
LC	liquid chromatography
LDH	lactate dehydrogenase
ln	natural logarithm
mg	milligram
Mg ⁺⁺	magnesium
min	minute
mL	milliliter
mmHg	millimeters of mercury
MTD	maximum tolerated dose
µg	microgram
N	number of subjects or observations
Na ⁺	sodium
N/A	not applicable
ng	nanogram
NIMP	non-investigational medicinal products
NSAID	nonsteroidal anti-inflammatory drug
PASI	Psoriasis Area and Severity Index
PD	pharmacodynamics
PK	pharmacokinetics
PO	per os (by mouth route of administration)
PT	prothrombin time
PTT	partial thromboplastin time

Term	Definition
Pu	percent of unbound drug
Q2D	Every other day
QC	quality control
QD, qd	quaque die, once daily
R ²	coefficient of determination
RBC	red blood cell
SAE	serious adverse event
SD	standard deviation
SOP	Standard Operating Procedures
sPGA	Static Physician's Global Assessment
Subj	subject
t	temperature
T	time
TAO	Trial Access Online, the BMS implementation of an EDC capability
T-HALF	Half life
T-HALF _{eff} _AUC	Effective elimination half life that explains the degree of AUC accumulation observed
T-HALF _{eff} _C _{max}	Effective elimination half life that explains the degree of C _{max} accumulation observed)
TID, tid	ter in die, three times a day
T _{max} , T _{MAX}	time of maximum observed concentration
TR_AUC(0-T)	AUC(0-T) treatment ratio
TR_AUC(INF)	AUC(INF) treatment ratio
TR_C _{max}	C _{max} treatment ratio
W	washout
WBC	white blood cell
WHO	World Health Organization
WOCBP	women of childbearing potential
x g	times gravity

APPENDIX 1 WOMEN OF CHILDBEARING POTENTIAL DEFINITIONS AND METHODS OF CONTRACEPTION

DEFINITIONS

Woman of Childbearing Potential (WOCBP)

A woman is considered fertile following menarche and until becoming post-menopausal unless permanently sterile. Permanent sterilization methods include hysterectomy, bilateral salpingectomy, and bilateral oophorectomy.

Women in the following categories are not considered WOCBP

- Premenarchal
- Premenopausal female with 1 of the following:
 - Documented hysterectomy
 - Documented bilateral salpingectomy
 - Documented bilateral oophorectomy

Note: Documentation can come from the site personnel's review of the participant's medical records, medical examination, or medical history interview.

- Postmenopausal female
 - A postmenopausal state is defined as 12 months of amenorrhea in a woman over age 45 years in the absence of other biological or physiological causes. In addition, females under the age of 55 years must have a serum follicle stimulating hormone, (FSH) level > 40 mIU/mL to confirm menopause.

Note: Females treated with hormone replacement therapy, (HRT) are likely to have artificially suppressed FSH levels and may require a washout period in order to obtain a physiologic FSH level. The duration of the washout period is a function of the type of HRT used. The duration of the washout period below are suggested guidelines and the investigators should use their judgement in checking serum FSH levels.

- 1 week minimum for vaginal hormonal products (rings, creams, gels)
- 4 week minimum for transdermal products
- 8 week minimum for oral products

Other parenteral products may require washout periods as long as 6 months. If the serum FSH level is > 40 mIU/ml at any time during the washout period, the woman can be considered postmenopausal.

CONTRACEPTION GUIDANCE FOR FEMALE PARTICIPANTS OF CHILD BEARING POTENTIAL

One of the highly effective methods of contraception listed below is required during study duration and until the end of relevant systemic exposure, defined as 3 days after the end of study treatment, plus 30 days

Local laws and regulations may require use of alternative and/or additional contraception methods.

Highly Effective Contraceptive Methods That Are User Dependent
 
Failure rate of <1% per year when used consistently and correctly.^a


 • Combined (estrogen- and progestogen-containing) hormonal contraception associated with inhibition of ovulation^b 
 – oral – intravaginal – transdermal

 • Progestogen-only hormonal contraception associated with inhibition of ovulation^b 
 – oral – injectable

Highly Effective Methods That Are User Independent

 • Implantable progestogen-only hormonal contraception associated with inhibition of ovulation^b • Intrauterine device (IUD)^c • Intrauterine hormone-releasing system (IUS)^c • Bilateral tubal occlusion

 • Vasectomized partner 
A vasectomized partner is a highly effective contraception method provided that the partner is the sole male sexual partner of the WOCBP and the absence of sperm has been confirmed. If not, an additional highly effective method of contraception should be used.

 • Sexual abstinence 
Sexual abstinence is considered a highly effective method only if defined as refraining from heterosexual intercourse during the entire period of risk associated with the study drug. The reliability of sexual abstinence needs to be evaluated in relation to the duration of the study and the preferred and usual lifestyle of the participant.
 
 • It is not necessary to use any other method of contraception when complete abstinence is elected. • WOCBP participants who choose complete abstinence must continue to have pregnancy tests, as specified in Section 5. • Acceptable alternate methods of highly effective contraception must be discussed in the

event that the WOCBP participants chooses to forego complete abstinence
NOTES: ^a Typical use failure rates may differ from those when used consistently and correctly. Use should be consistent with local regulations regarding the use of contraceptive methods for participants participating in clinical studies. ^b Hormonal contraception may be susceptible to interaction with the study drug, which may reduce the efficacy of the contraceptive method. Hormonal contraception is permissible only when there is sufficient evidence that the IMP and other study medications will not alter hormonal exposures such that contraception would be ineffective or result in increased exposures that could be potentially hazardous. In this case, alternative methods of contraception should be utilized. ^c Intrauterine devices and intrauterine hormone releasing systems are acceptable methods of contraception in the absence of definitive drug interaction studies when hormone exposures from intrauterine devices do not alter contraception effectiveness

Less Than Highly Effective Contraceptive Methods That Are User Dependent Failure rate of >1% per year when used consistently and correctly.

• Male or female condom with or without spermicide. Male and female condoms cannot be used simultaneously• Diaphragm with spermicide• Cervical cap with spermicide• Vaginal Sponge with spermicide• Progestogen-only oral hormonal contraception, where inhibition of ovulation is not the primary mechanism of action
Unacceptable Methods of Contraception

• Periodic abstinence (calendar, symptothermal, post-ovulation methods)• Withdrawal(coitus interruptus).• Spermicide only• Lactation amenorrhea method (LAM)

CONTRACEPTION GUIDANCE FOR MALE PARTICIPANTS WITH PARTNER(S) OF CHILD BEARING POTENTIAL.

Male participants with female partners of childbearing potential are eligible to participate if they agree to the following during the treatment and until the end of relevant systemic exposure.

- Inform any and all partner(s) of their participation in a clinical drug study and the need to comply with contraception instructions as directed by the investigator.

- Male participants are required to use a condom for study duration and until end of relevant systemic exposure defined as 3 days after the end of treatment plus an additional 90 days.
- Female partners of males participating in the study to consider use of effective methods of contraception until the end of relevant systemic exposure, defined as 3 days after the end of treatment in the male participant.
- Male participants with a pregnant or breastfeeding partner must agree to remain abstinent from penile vaginal intercourse or use a male condom during each episode of penile penetration during the treatment and until 3 days after the end of treatment.
- Refrain from donating sperm for the duration of the study treatment and until 3 days after the end of treatment.

COLLECTION OF PREGNANCY INFORMATION

Guidance for collection of Pregnancy Information and outcome of pregnancy on the Pregnancy Surveillance Form is provided in [Section 6.4](#) and the Appendix for Adverse Events and Serious Adverse Events Definitions and procedures for Evaluating, Follow-up and Reporting

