3.3 Study Population

For entry into the study, the following criteria MUST be met prior to dosing on Day 1. No exceptions will be granted.

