3.3.1 Inclusion Criteria

1. Signed Written Informed Consent

- a) Subjects is willing to participate in the study and has signed the informed consent

2. Target Population

- a) Male and female subjects with a diagnosis of plaque psoriasis for ≥ 6 months
- b) Body mass index (BMI) 18-40 kg/m² and total body weight > 50 kg (110 lb)
- c) Deemed by Investigator to be eligible for phototherapy or systemic therapy
- d) Psoriatic plaques must cover $\geq 10\%$ of body surface area (BSA)
- e) Psoriasis Area and Severity Index (PASI) score ≥ 12 and sPGA ≥ 3

3. Age and Reproductive Status

- a) Males and Females, ages 18 or age of majority to 70 years, inclusive
- b) Women of childbearing potential (WOCBP) must have a negative serum or urine pregnancy test (minimum sensitivity 25 IU/L or equivalent units of HCG) within 24 hours prior to the start of study drug.
- c) Women must not be pregnant, lactating, breastfeeding or planning pregnancy during the study period
- d) Women of childbearing potential (WOCBP) must agree to follow instructions for method(s) of contraception for the duration of treatment with study drug(s) BMS-986165 plus 5 half-lives of study drug plus 30 days (duration of ovulatory cycle) for a total of 33 days post-treatment completion
- e) Males who are sexually active with WOCBP must agree to follow instructions for method(s) of contraception for the duration of treatment with study drug(s) BMS-986165 plus 5 half-lives of the study drug plus 90 days (duration of sperm turnover) for a total of 93 days post-treatment completion. In addition, male subjects must be willing to refrain from sperm donation during this time.
- f) Azoospermic males are exempt from contraceptive requirements. WOCBP who are continuously not heterosexually active are also exempt from contraceptive requirements, and still undergo pregnancy testing as described in this section.

Investigators shall counsel WOCBP and male subjects who are sexually active with WOCBP on the importance of pregnancy prevention and the implications of an unexpected pregnancy. Investigators shall advise on the use of highly effective methods of contraception ([Appendix 1](#)) which have a failure rate of < 1% when used consistently and correctly.

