- c) Chest X-ray findings suspicious of infection at screening. Subjects may be rescreened if deemed eligible may be randomized within 28 days of completing an appropriate course of antibiotic treatment for pulmonary infection.
- d) Leukopenia defined as absolute WBC count $< 3000/\text{mm}^3$ within 28 days of dosing with study drug on Day 1
- e) Lymphopenia defined as absolute lymphocyte count $< 500/\text{mm}^3$ within 28 days of dosing with study drug on Day 1
- f) Neutropenia defined as absolute neutrophil count $< 1000/\text{mm}^3$ within 28 days of dosing with study drug on Day 1
- g) Moderate to severe thrombocytopenia defined as platelet count $< 100,000/\text{mm}^3$ within 28 days of dosing with study drug on Day 1
- h) Moderate to severe anemia defined as hemoglobin $< 9 \text{ g/dL}$ within 28 days of dosing with study drug on Day 1
- i) ALT and/or AST $> 3\text{X ULN}$ within 28 days of dosing with study drug on Day 1
- j) Total, unconjugated, and/or conjugated bilirubin $> 2\text{X ULN}$ within 28 days of dosing with study drug on Day 1
- k) Any other significant laboratory or procedure abnormalities that, in the opinion of the Investigator, might place the subject at unacceptable risk for participation in this study

8. Allergies and Adverse Drug Reaction

- a) History of any significant drug allergy (such as anaphylaxis or hepatotoxicity)

9. Other Exclusion Criteria

- a) Prisoners or subjects who are involuntarily incarcerated. (Note: under certain specific circumstances a person who has been imprisoned may be included or permitted to continue as a subject. Strict conditions apply and Bristol-Myers Squibb approval is required.
- b) Subjects who are compulsorily detained for treatment of either a psychiatric or physical (e.g., infectious disease) illness
- c) Inability to comply with restrictions and prohibited activities/treatments as listed in Section 3.4

Eligibility criteria for this study have been carefully considered to ensure the safety of the study subjects and that the results of the study can be used. It is imperative that subjects fully meet all eligibility criteria.

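### Appendix 1 ends the male sperm-donation restriction 3 days after treatment, but inclusion criterion 3e requires 93 days

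*Protocol*

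**What the plan says.** **Inclusion criterion 3e (Protocol Section 3.3.1).** Men who are sexually active with women of childbearing potential (WOCBP) must use contraception during treatment and afterwards "for a total of 93 days post-treatment completion. In addition, male subjects must be willing to refrain from sperm donation during this time".

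**Appendix 1, guidance for male participants.** The list opens by saying that men with partners of childbearing potential "are eligible to participate if they agree to the following during the treatment and until the end of relevant systemic exposure". Four of its bullets state a duration:

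- Condom use runs "until end of relevant systemic exposure defined as 3 days after the end of treatment plus an additional 90 days".
- Female partners are asked to consider contraception "until the end of relevant systemic exposure, defined as 3 days after the end of treatment in the male participant".
- Men with a pregnant or breastfeeding partner must abstain or use a condom until 3 days after treatment.
- On sperm donation: "Refrain from donating sperm for the duration of the study treatment and until 3 days after the end of treatment".

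**Status of the criteria.** Section 3.3 says: "For entry into the study, the following criteria MUST be met prior to dosing on Day 1. No exceptions will be granted". Section 3.3.2 closes with: "It is imperative that subjects fully meet all eligibility criteria".

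**The concern.** The same protocol gives two end dates for one reproductive-safety restriction. Criterion 3e explains its longer period by sperm turnover. The Appendix 1 bullet leaves that period out and gives no reason for doing so.

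At stake is what a man is told once dosing stops. Criterion 3e is checked before Day 1, as a willingness to comply. The restriction itself has to be observed after the last dose, and a site that looks up Appendix 1 at that point will find 3 days.

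**Working it through.** **Inputs**

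- Male contraception and sperm-donation period in 3e: "5 half-lives of the study drug plus 90 days (duration of sperm turnover) for a total of 93 days post-treatment completion".
- Contraception period for women in criterion 3d: 5 half-lives plus 30 days, 33 days in total.
- Appendix 1: 3 days for sperm donation; 3 + 90 days for condoms.
- Last scheduled visit: Day 115 (Section 3.1).

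**Step 1. Reproduce the 93 days.** Five half-lives = 93 − 90 = 3 days. The rule for women gives the same: 33 − 30 = 3 days. Appendix 1 also puts the end of systemic exposure at 3 days. So 3 + 90 = 93 days, and 3e is internally sound.

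**Step 2. Size the conflict.** 93 − 3 = 90 days, which equals the sperm-turnover period in 3e.

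**Step 3. Decide which text looks wrong.** The Appendix 1 condom bullet gives 3 + 90 = 93 days and agrees with 3e. The sperm-donation bullet therefore departs both from 3e and from the rationale of a neighbouring bullet.

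**Step 4. Place it on the study calendar.** Assume the last dose is on Day 85.

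| Text | Restriction ends | Position at Day 115 |
|---|---|---|
| Appendix 1 | 85 + 3 = Day 88 | ended 115 − 88 = 27 days earlier |
| Criterion 3e | 85 + 93 = Day 178 | 178 − 115 = 63 days remain |

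The Day 85 visit has a window of ±7 days. If the last dose moves with it (Day 78 to Day 92), Appendix 1 ends the restriction between Day 81 and Day 95, and 3e between Day 171 and Day 185. The gap stays at 90 days. These dates only illustrate the conflict. The 93-day condom rule, which is not in dispute, also runs past Day 115.

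**Step 5. Look for a text that settles it.** Section 3.4.3, on other restrictions and precautions, covers only sun exposure. The protocol's document history lists only the original version, and SAP Section 2.4 lists no amendments, so neither sentence is superseded. No precedence rule appears in either document.

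**Step 6. Check the other two 3-day bullets against 3e.**

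- The female-partner bullet advises the partner. Criterion 3e binds the man, so that bullet does not restate it.
- The pregnant or breastfeeding partner bullet is less clear. The WOCBP definitions in Section 3.3.3 and Appendix 1 turn on menarche, sterilisation and menopause, and do not exclude a pregnant or breastfeeding woman. Read literally, her partner falls under the 93 days of 3e, while the bullet gives him 3. It may be a deliberate exception, but the documents do not say so.

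**The case against.** The strongest reply is that 3e already controls. It is mandatory without exception, and a man who refrains for 93 days satisfies both texts. Condom use agrees at 93 days in both places. The documents do not show that any site would counsel from the shorter text, and the consent form may already state 93 days. Nothing statistical depends on it.

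Most of this stands, and it keeps the point minor. It does not remove the conflict, because 3e secures a commitment at entry and does not govern later advice.

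Two narrower readings are tempting and are not supported:

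- *The risk is confined to sites that use Appendix 1 alone.* The Appendix 1 list is itself worded as an eligibility condition and nothing says which text prevails, so a site that reads both still has two end dates.
- *Sperm donation is the only bullet that conflicts with a criterion.* The WOCBP definitions leave the pregnant or breastfeeding partner bullet open.

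Two stronger readings also go too far:

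- *Section 3.3.1 directs sites to the 3-day rule.* Its reference to Appendix 1 concerns effective methods of contraception. It makes Appendix 1 a natural source for counselling, but says nothing about how long to avoid sperm donation.
- *Men will be released early, with reproductive harm.* The documents give no frequency of sperm donation and no reproductive-risk figure.

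**Conclusion.** The contradiction is real in current text: 3 days against 93, a 90-day difference on sperm donation. The Appendix 1 bullet appears to be the one in error, since 3e and the condom bullet share the same 3 + 90 construction.

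The calendar dates assume a last dose on Day 85; the 90-day gap does not depend on that. Whether participants would actually be misinformed cannot be judged, because the consent text was not available. There is no effect on design, sample size, power or analysis. This is a minor wording correction that serves a reproductive-safety purpose.

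**What to change.** Revise the Appendix 1 sperm-donation bullet to match 3e, for example: *Do not donate sperm during study treatment or for 93 days after it ends (3 days of remaining exposure plus 90 days for sperm turnover).* Check that the consent text states the same period.

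In the same revision, ask the clinical team to review two related items:

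- **The lead-in to the male list.** It refers to the end of systemic exposure, which the female-partner bullet defines as 3 days. A corrected 93-day bullet would otherwise sit under a sentence that can still be read as 3 days.
- **The pregnant or breastfeeding partner bullet.** Either state that it is an exception to 3e or extend it to 93 days.

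The cost is a few lines of protocol text. Section 9.1.1 describes two routes: an amendment with IRB/IEC approval, or an administrative letter of which the IRB/IEC is informed. The SAP needs no change.
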